Study Protocol and Statistical Analysis Plan

The Effect of IV NSAID's and Corticosteroids on Dysphasia and Dysphonia Following ASDF

NCT04650893

Recent Date of Approval: 1/19/2023

Study Protocol

Background & Rationale

Dysphagia and dysphonia are the most common postoperative complications following anterior cervical discectomy and fusion (ACDF). While most postoperative dysphagia and dysphonia is transient, severe cases place the patient at risk for malnutrition, aspiration, pneumonia, airway obstruction, persistent cough, and death. The reported prevalence of dysphagia varies from 3% to 67% and dysphonia from 1% to 51%. The variability is a result of the different ways in which dysphagia and dysphonia are measured and defined. There are many different classification systems for dysphagia, the Eating Assessment Tool-10 (EAT-10) has proven to be reliable, valid, treatment-responsive, and multiculturally versatile. Scores of 3 or greater qualify as clinically relevant dysphagia and scores of 15 or greater qualify as severe dysphagia, which is associated with a higher risk of aspiration. The Voice Handicap Index-10 (VHI-10) has proven to be reliable, valid, and expedient tool to evaluate for dysphonia. Scores greater than 11 are indicative of clinically significant dysphonia. Recent research suggests that these are appropriate patient reported outcome measures (PROMs) to evaluate for dysphagia and dysphonia after cervical spine surgery. Local and intravenous (IV) steroids have been shown to reduce dysphagia and prevertebral soft-tissue swelling following ACDF. A recent study compared the efficacy of local versus intravenous steroids on the likelihood of developing dysphagia and dysphonia after ACDF. It found that both yielded better PROMs for dysphagia compared the control group, with a reduced number of patients reporting severe dysphagia with local steroid application within the first 2 weeks post-op. Local corticosteroids have been associated with impaired wound healing, esophageal complications, and pseudoarthrosis, particularly when administered in the retropharyngeal space. In the study mentioned above, 2 patients in the local corticosteroid group (out of 29 total) developed pseudoarthrosis. Perioperative ketorolac has been shown to have no adverse effect on spinal fusion when administered for < 2 days, or for >2 days at a dose of < 120 mg/day. Current standard of care processes include both IV or local steroid use as well as no steroid use in decreasing the risks of dysphagia or dysphonia post operatively. There are no current specific or routinely used methods in using steroid or no steroidal treatments to those receiving this surgical procedure.

Objectives

The purpose of this study is to assess the efficacy of intraoperative intravenous nonsteroidal antiinflammatory drug (ketorolac) versus intravenous (dexamethasone) administration on dysphagia and dysphonia after ACDF. Primary measures for dysphagia include the classification of the Bazaz and EAT-10 outcome results. The primary measures for Dysphonia will be analyzed by the Voice Handicap Index (VHI-10). Secondary measurements include result classification utilizing results from the Neck Disability Index(NDI) and Visual Analogue Pain Scale (VAS) for neck pain. Additional measurements to be analyzed are comparisons in complication factors in surgical site infection, need for re-operation and pseudoarthrosis.

Design

An on-line randomization generator will be used www.researchrandomizer.org.

Randomization will be an equal split between the three groups with no predictable pattern. The subject has a one in three chance of being randomized to any of the three different groups.

Subjects are blinded to the randomization assignment. This is a single blinded study. The treating physician and study personnel will know which group the subject is randomized into.

The lead study coordinator will track the randomization assignments, withdrawals and study completions. Once 25 from each of the 3 groups have completed the study, the study will cease enrollment.

Methods

Each study participant will have equal chance of being assigned to one of the three study groups. The subjects medical record will be reviewed and the data collected/documented will include: gender, age, diagnosis or reason for surgery, co-morbidities, medications, BMI pre-operative and post-operatively. All clinic follow-up progress notes will be reviewed to specifically collect any findings documented as complications from surgery.

Subjects who elect to consent into the study will be assigned a random study number and randomized into three cohorts: control (no steroid or NSAID), IV NSAID (1-time dose of 30 mg of IV ketorolac at the time of closure), and IV steroid (1-time dose of 10 mg of IV dexamethasone at the time of closure). Randomization schedule will be performed in a 1:1:1 fashion. Patients will be blinded with regard to which treatment they received until at least 1 year after surgery. Those subjects whom willingly volunteer to be part of the study will be notified promptly if they are found to not meet trial criteria and advised that they will be automatically withdrawn from the study.

Patient outcomes (patient completed questionnaires to evaluate for dysphagia and dysphonia) will be collected preoperatively and at 1 day (post-surgical day to day 3 post-op), 3 weeks (+/- one week), 6 weeks (+/- two weeks), 3 months (+/- three weeks), 6 months (+/- one month), and 1 year (+/- three months) postoperatively and will include: The Eating Assessment Tool (EAT-10), The Voice Handicap Index (VHI-10), Neck Disability Index (NDI), and Visual Analogue Pain Scale (VAS), Bazaz classification for dysphagia.

Post operative questionnaire collection will occur at time of outpatient clinic follow-up or subject may be called by phone and data collected over the phone or questionnaires mailed if patient preference. (Clinic visit follow up per the usual standard of medical care is per the above data collection timeline points, however, many times patients are feeling better and do not return for all suggested follow-up).

Eligibility

Inclusion

>/= 19 years of age Undergoing ACDF for radiculopathy or myelopathy No known allergies or sensitivities to steroid or non-steroidal medications This is not an ACDF revision procedure or surgery related to treatment of trauma, infection or tumor.

Exclusion

Procedure is being done for revision, trauma, infection or tumor. Patients with known diagnosed metabolic diseases (diabetes, pancreatitis, gout, electrolyte imbalances, hypertension, hematological abnormalities including gastrointestinal bleeding...) Patients with known kidney disease or a creatinine level above the upper limit of normal > 1.27) (BMet labs are completed pre-operatively as standard of care on all patients unless there is documentation of normal labs completed within the past 6 months of surgery).

Patients with known allergy or sensitivities to steroid or non-steroidal medications

Statistical Analysis Plan

For dysphagia, primary outcome measures will be the Bazaz classification and the EAT-10. For dysphonia, primary outcomes will be measured by the VHI-10. Secondary outcomes will be measured with Neck Disability Index (NDI), Visual Analogue Pain Scale (VAS) for neck pain. Complications will also be documented for comparison to include: surgical site infection, need for reoperation and pseudoarthrosis.

Descriptive statistics (specifically counts and percentages) will be computed for all variables to ensure data quality and to evaluate the assumptions of statistical tests. Fisher's exact test will be used to evaluate associations between treatment groups and categorical measures at each time point. Analysis of variance (ANOVA) or the Kruskal-Wallis test, depending on the distribution of the data, will be utilized to compare continuous variables between the groups. If the overall p-value from ANOVA is statistically significant, pairwise comparisons will be performed and adjusted using Tukey's method. Mixed effect models also will be explored, with time, treatment group, and time x treatment group interaction terms as fixed effects and with a random intercept term to account for repeated measures All tests will be 2-sided and a p-value < 0.05 will be considered statistically significant.

No analysis was ultimately completed due to poor follow-up and lack of data.

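### The plan lets the operating surgeon know the arm during surgery, although the study treatment as described is not due until closure: an avoidable opening for performance bias

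*Combined protocol and SAP*

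**What the plan says.** The Design section of the combined protocol and SAP sets the level of blinding: "Subjects are blinded to the randomization assignment. This is a single blinded study". It continues: "The treating physician and study personnel will know which group the subject is randomized into". It gives no starting point for that knowledge and places no restriction on it. The same section has the lead study coordinator keep track of the assignments.

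The Methods section describes allocation as following consent: "Subjects who elect to consent into the study will be assigned a random study number and randomized into three cohorts". One arm receives a single ketorolac dose and another a single dexamethasone dose, both timed to closure; the entry for the latter reads "IV steroid (1-time dose of 10 mg of IV dexamethasone at the time of closure"). The control arm receives neither drug, and no placebo is described.

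The Methods section lists the data taken from the medical record as "gender, age, diagnosis or reason for surgery, co-morbidities, medications, BMI pre-operative and post-operatively", and complications are collected from follow-up notes. No operative variable is listed.

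The Statistical Analysis Plan states: "For dysphagia, primary outcome measures will be the Bazaz classification and the EAT-10". VHI-10 is primary for dysphonia. The exploratory mixed model has time, treatment group and their interaction as its fixed effects.

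**The concern.** As described, the three arms are treated alike until closure. Anyone who learns the assignment earlier gains knowledge that delivering the treatment does not call for. The outcomes are swallowing and voice complaints after an operation on the neck, so it is reasonable to ask whether a surgeon who knows that a patient will or will not receive an anti-inflammatory drug might work differently before that point.

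Any such difference would reach all three primary measures and could not be separated from the effect of the drug. Blinding the patient protects the way the questionnaires are answered. It does not protect against something done in the operation before the patient answers any postoperative questionnaire.

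**Working it through.** **Reading the sections together**

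1. Who knows: the treating physician and study personnel (Design). The text does not say that the treating physician is the operating surgeon. I assume that this is at least sometimes so.
2. From when: not stated. Allocation is described after consent (Methods), and no step holds the assignment back until surgery or closure.
3. When the arms diverge: at closure, in all three arms (Methods).
4. Is earlier knowledge needed? Not for the intervention as described. The documents are silent on ordering and preparing the drug, so some advance preparation may be needed. That can be met by having both drugs to hand.
5. Other safeguards: operative technique is not standardised. The listed data contain no operative variable, such as levels fused or operative time, so a difference between arms in such a variable could not be seen in those data. The mixed model has no term that could adjust for one.

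Steps 1 to 3 show that knowledge of the arm during the operation is permitted. They do not show that it occurs.

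**Illustration of scale, purely assumed**

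The plan gives no effect size, SD or power calculation, so there is no figure of its own to reproduce. The inputs from the documents are 25 completers per arm (Design) and a two-sided 0.05 level (Statistical Analysis Plan). The assumed input is a shift of b SD in one arm caused by operative handling, with no drug effect and normal data. No value of b comes from the documents.

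- *Unadjusted comparison of two arms, normal approximation.* The standard error is √(2/25) = 0.283 SD, and the rejection probability is P(|Z + b/0.283| > 1.96). For b = 0.2, b/0.283 = 0.707, giving 10.9%. For b = 0.3 it is 1.061, giving 18.6%. The noncentral t distribution with 48 degrees of freedom gives 10.7% and 18.0%.
- *Three-group ANOVA, the plan's first step for continuous outcomes.* The noncentrality is 25 × b² × 2/3, which is 0.667 for b = 0.2 and 1.5 for b = 0.3. With 2 and 72 degrees of freedom the rejection probability is 10.1% and 17.3%.
- *One named pair that includes the shifted arm, after a significant ANOVA and with Tukey's adjustment.* By simulation, about 5% and 9%. With b = 0 the same rule gives about 2%.

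These figures show what an assumed bias would do at this sample size. They would be the same for a bias from any other source, and they are not an estimate for this trial.

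**The case against.** The strongest reply is that the chain from knowledge to bias has no support in the documents. The Background calls dysphagia and dysphonia the most common complications after this operation and says that steroids reduce dysphagia and prevertebral swelling, but it names no operative step as a cause. It also describes IV steroid, local steroid and no steroid as all within current care. Surgeons may therefore be used to operating with and without cover, which makes a change of technique less likely. The direction is open too: extra care in control patients would shrink a true drug effect and not create a false one. Finally, the single-blind design is openly declared, the outcomes are completed by the patient, and patients stay blinded for at least a year.

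Most of this stands, and it limits the point to a possibility. A reader might infer that the surgeon does know the arm before closure, that retraction or implant work differs by arm, or that false positives run at 10 to 18%. The documents support none of these. They set no time of disclosure, do not mention those steps, and give no basis for a shift of 0.2 or 0.3 SD. The percentages also overstate the planned pairwise claim, which is Tukey-adjusted.

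The reply does not touch the gap itself. A declared single-blind design settles that the physician may know the arm, but not when. Patient blinding guards against biased reporting only, and nothing else in the plan closes this route.

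**Conclusion.** The point holds as a cheap improvement. The plan permits the arm to be known during the operation, when the treatment as described does not require it, and so leaves open a possibility of performance bias on all three primary measures. Neither its size nor its direction can be estimated from the documents.

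The conclusion rests on two assumptions: that the treating physician is or includes the operating surgeon, and that operative handling can affect swallowing and voice. Nothing in the plan is contradicted, and nothing shows that bias occurred. The Statistical Analysis Plan reports that no analysis was completed because follow-up was poor and data were lacking, so no reported result is affected. The practical use of the point is for a restart or a successor with the same design.

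**What to change.** Add to the Design section that the lead study coordinator, or a sealed envelope, holds the assignment and that it is released in the operating room only when closure begins. The operating team stays unaware until then, and the time of release is recorded. The treating physician may know the arm afterwards, as the plan now allows, so the trial remains single blind.

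The cost is a wording change and one extra step in the operating room, and both study drugs must be available at closure. It needs no extra staff, adds nothing for the patient, and leaves the treatments and their timing as they are.

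### The only source named for complications depends on clinic attendance, which the protocol expects to be incomplete; events are likely to be missed, with a bias of uncertain size and direction

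*Combined protocol and SAP*

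**What the plan says.** On the source of complication data, the Methods state: "All clinic follow-up progress notes will be reviewed to specifically collect any findings documented as complications from surgery". The wider record review in the same section is described as "The subjects medical record will be reviewed and the data collected/documented will include: gender, age, diagnosis or reason for surgery, co-morbidities, medications, BMI". The items listed there are descriptive; complications, readmissions and care elsewhere are not among them.

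On attendance, the Methods remark that "many times patients are feeling better and do not return for all suggested follow-up". For patients who do not attend, "subject may be called by phone and data collected over the phone or questionnaires mailed if patient preference". That route is given for collecting the questionnaires: EAT-10, VHI-10, NDI, VAS and Bazaz. The plan attaches no question on infection, reoperation or fusion to these contacts.

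On use, the Objectives say: "Additional measurements to be analyzed are comparisons in complication factors in surgical site infection, need for re-operation and pseudoarthrosis". The Statistical Analysis Plan repeats the commitment: "Complications will also be documented for comparison to include: surgical site infection, need for reoperation and pseudoarthrosis". The test is given as "Fisher's exact test will be used to evaluate associations between treatment groups and categorical measures at each time point". Neither part gives a denominator for complication rates, a rule for missed visits or a definition of pseudoarthrosis.

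**The concern.** The plan foresees that patients will miss visits and solves this for the questionnaires, but not for complications. Whether an event is captured then depends on whether the patient came back. The protocol ties that to how the patient feels, which the treatments are meant to influence, so return could differ by arm. The Design section adds a second possible route to unequal recording: the treating physician and study personnel know the allocation.

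What is at stake is the comparison of infection, reoperation and pseudoarthrosis. The Background raises pseudoarthrosis as a harm of local corticosteroids and discusses ketorolac and fusion, so a reader will look for this comparison. Pseudoarthrosis is also the listed event most easily missed when a patient who feels well stays away.

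**Working it through.** The plan states no complication rate or return rate for this trial, so there is no figure of its own to reproduce. What follows shows how the mechanism behaves under stated assumptions.

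**Inputs.** From the documents: 25 completers per group (Design); two-sided 0.05 (Statistical Analysis Plan); 2/29 = 6.9% pseudoarthrosis in the local-steroid arm of a cited study (Background). That arm is not in this trial, so 6.9% is illustrative only, with 5% to 10% as a range. Assumed: capture between 50% and 100%, and the same true risk in all arms.

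**Step 1: equal capture.** Recorded events per arm = 25 × risk × capture. At full capture: 25 × 0.069 = 1.72 per arm, 5.17 in all. At 70% capture in every arm: 1.21 per arm, 3.62 in all. Events are lost, but no arm difference appears.

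**Step 2: unequal capture.** With capture of 90%, 70% and 50%, recorded events are 1.55, 1.21 and 0.86. The ratio between the extreme arms is 0.9/0.5 = 1.8, and the difference is 6.9% × (0.9 − 0.5) = 2.8 percentage points (2.0 at 5% risk, 4.0 at 10%). The chance of recording no event in an arm of 25 is (1 − 0.069)^25 = 17% at full capture and (1 − 0.0345)^25 = 42% at 50% capture.

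**Step 3: who stays away.** Suppose 60% return and non-returners have r times the risk of returners, with overall risk fixed at 6.9%. Share captured = 0.6/(0.6 + 0.4r). Rate among returners = 6.9%/(0.6 + 0.4r).

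| r | Events captured | Rate over all randomised | Rate over returners only |
|---|---|---|---|
| 1 | 60% | 4.1% | 6.9% |
| 0.5 | 75% | 5.2% | 8.6% |
| 0.25 | 86% | 5.9% | 9.9% |
| 0 | 100% | 6.9% | 11.5% |

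The true rate is 6.9% in every row. The all-randomised rate is too low or right; the returners-only rate is right or too high. The direction of the error depends on a denominator that the plan does not fix.

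**Step 4: significance.** In a pairwise Fisher test at 25 v 25, 5 v 0 events give p = 0.0502 and 6 v 0 give p = 0.022. If the test is run across all three arms, which the plan's wording allows, 4, 0 and 0 events give p = 3 × C(25,4)/C(75,4) = 3 × 12,650/1,215,450 = 0.031. Summing the probabilities of all significant three-arm tables at 6.9% risk gives a false-positive rate of 2.1% at full capture and 1.9% at 90/70/50 capture; at 10% risk, 3.0% and 3.4%. Either way it stays below 5%.

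Hiding a real difference is the more likely harm. For true risks of 20% v 5%, pairwise Fisher power is 19.8% at full capture. If the higher-risk arm is captured at 50% and the other at 90% (10% v 4.5% recorded), it is 1.4%.

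**The case against.** The strongest case on the other side has several parts.

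- **A reader might infer that a patient without a late note is counted as event-free.** The documents contain no such rule; they are silent on how an absent note is coded. This stands.
- **A reader might infer that every rate is understated.** The protocol's own reason for non-return is feeling better, which suggests lower risk in those who stay away, and patients with a symptomatic infection are likely to come back. Step 3 shows that the loss then shrinks and that a returners-only rate errs upwards. This stands, and it leaves late, silent or externally treated events as the main loss.
- **A reader might infer that the plan would produce a false significant difference between arms.** No return rates by arm are given, and Step 4 shows that significance would seldom result. Even non-return of 20% v 50% at 6.9% risk gives 1.38 v 0.86 expected events, about half an event. This stands.
- **Notes are the only source named, but the plan does not say they are exclusive.** The record review lists what it will include, and a reoperation at the same centre could surface there. Patients are said to miss some visits, not all, so a later note can record an earlier event. Enrolment also continues until 25 per group complete, although completion is not defined. These points soften the gap but do not close it.
- **Complications are additional measures, and chart review is a common low-cost choice for them.** This is true and limits the priority. It does not explain why contacts already planned should not ask about complications.

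**Conclusion.** The point holds in a limited form. The one source named for complications depends on attendance, the protocol expects attendance to be incomplete for a reason related to outcome, and the remote route does not extend to complications. Some late, silent or externally treated events are likely to be missed, and capture may differ by arm if return does.

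Size and direction are uncertain. Under the assumed figures the distortion is about 2 to 4 percentage points between the extreme arms, or less than one event per arm of 25. It affects estimates far more than significance tests. These figures rest on assumed capture rates and on a risk borrowed from an arm outside this trial.

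A reader might also take this as a fault in a published safety result. The Statistical Analysis Plan records that no analysis was completed, because of poor follow-up and lack of data. The weakness is therefore in the plan, and it bears on any complication counts reported later or on a follow-on study that reuses the design. It is worth correcting mainly because the correction is cheap.

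**What to change.** **In the Methods.** At every planned contact, including phone and mail, ask a short scripted question on the listed complications: infection treated, reoperation anywhere, told that the fusion had not healed. Check positive answers against the record. Search the full medical record, not just the clinic notes, for all randomised patients.

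**In the Statistical Analysis Plan.** Do not code an absent note as no event. For each arm, report the events, the number with known status and the number unknown. Show each rate over all randomised patients and over those with known status, as bounds. The first is a floor for verified events; the second serves as an upper bound only if patients of unknown status are at no greater risk than those assessed, and the text should say so.

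**For pseudoarthrosis.** Report it descriptively with the number whose fusion status was documented, and note that this rate may be too high if well patients are not assessed. No extra imaging is needed for this.

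**Cost.** A few questions added to contacts already planned, a wider record search, verification of self-reports and a short reporting rule in the analysis plan. Arm differences in who has fusion status documented would remain, so the pseudoarthrosis comparison would still need cautious reading.

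### A caller who knows the arm may take the patient-reported primary outcomes by phone, because the plan unblinds study personnel and does not say who calls

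*Combined protocol and SAP*

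**What the plan says.** The Design section of the protocol sets out the blinding: "Subjects are blinded to the randomization assignment. This is a single blinded study". It adds: "The treating physician and study personnel will know which group the subject is randomized into". No group of study personnel is excepted. Under Methods, the patient's own blinding is to last a year or more: "Patients will be blinded with regard to which treatment they received until at least 1 year after surgery".

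Methods describes the outcomes as "patient completed questionnaires to evaluate for dysphagia and dysphonia". For post-operative collection it allows three routes: at the clinic visit, by telephone ("subject may be called by phone and data collected over the phone"), or by post ("or questionnaires mailed if patient preference"). It expects missed visits, noting that "many times patients are feeling better and do not return for all suggested follow-up".

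The Statistical Analysis Plan makes these questionnaires primary: "For dysphagia, primary outcome measures will be the Bazaz classification and the EAT-10". VHI-10 is primary for dysphonia.

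The documents do not say who telephones. They provide no caller kept unaware of the arm, no call script, no record of how each form was obtained, and no reporting by mode.

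**The concern.** A form that is read out and written down by someone else is no longer completed by the patient. The caller can paraphrase an item, prompt, or decide how to code a hesitant answer. If the caller knows the arm, those small decisions can differ by arm, and the difference goes straight into the treatment contrast. Blinding the patient controls the patient's expectation but not the caller's. The Background section tells staff that steroids have been shown to reduce dysphagia, so an expectation about at least one arm is plausible.

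All three primary outcomes can be collected this way. The exposure is also avoidable: a person reading out a questionnaire has no evident need to know the assignment, and the documents give no reason for telling them.

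**Working it through.** **1. Reading the sections together.** Design: study personnel know the arm. Methods: post-operative questionnaire data may be taken by phone, caller not named. Statistical Analysis Plan: those questionnaires are the primary outcomes. It follows that the plan permits a caller who knows the arm. It does not follow that every caller would know it, or that any caller would act on it.

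**2. Is there a figure to reproduce?** No. The documents give no SD, effect size or power, no share of forms by phone, and no estimate of interviewer effect. What follows is an illustration.

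**3. Inputs.**
- From the documents: 25 completers per arm in three arms (Design); ANOVA as one of the two planned tests for continuous measures, two-sided 5% level (Statistical Analysis Plan).
- Assumed: no true effect; a share *f* of forms by phone, the same in every arm; an average shift of *b* SD per call in one arm and none in the other two. Values tried: *f* = 0.25, 0.5, 1 and *b* = 0.1, 0.2, 0.3, 0.5.

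**4. Formula.** The arm means in SD units are (*fb*, 0, 0), with overall mean *fb*/3. The squared deviations sum to (2/3)(*fb*)². The noncentrality is λ = 25 × (2/3)(*fb*)² = 16.67(*fb*)². The false-positive rate is the probability that a noncentral F with 2 and 72 degrees of freedom and noncentrality λ exceeds the 5% critical value of the central F. With *fb* = 0 it is 5.0%, as it should be. The result is the same whichever arm carries the shift.

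**5. Results.**

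| Share by phone *f* | *b* = 0.1 | *b* = 0.2 | *b* = 0.3 | *b* = 0.5 |
|---|---|---|---|---|
| 0.25 | 5.1% | 5.3% | 5.7% | 6.9% |
| 0.5 | 5.3% | 6.2% | 7.8% | 13.3% |
| 1 | 6.2% | 10.1% | 17.3% | 41.5% |

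Worked corners: for *f* = 0.25 and *b* = 0.1, *fb* = 0.025 and λ = 0.010, giving 5.1%. For *f* = 1 and *b* = 0.5, *fb* = 0.5 and λ = 4.17, giving 41.5%.

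**6. Reading the table.** The rate stays near nominal if calls are few or the shift per call is small, and becomes material only if the phone is the main route and the shift is sizeable. The plan does not record mode, so nobody could tell afterwards which row applied. The table covers one continuous outcome at one time point.

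**7. With the fix.** If the caller does not know the arm, or the patient completes the form, the shift due to the caller's knowledge is zero and the rate returns to 5.0%.

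**The case against.** **The caller is not identified.** A reader might infer that the interviewer is unblinded by design. The documents do not go that far: they unblind study personnel and leave the caller unnamed. The point is therefore what the plan permits.

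**The patients are blinded and answer named questionnaires.** This stands, and it limits the route of bias to the caller's prompting, wording or recording. Such behaviour is possible but not shown.

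**The size can be made to look large.** With 25 per arm, an assumed SD of 5 and a 2-point shift in mean EAT-10, a single pairwise comparison has a false-positive rate of 29%. A reader might take that as the likely effect. It applies the shift to the whole arm, as if every form came by phone. If a quarter did, a 2-point mean shift would need 2/0.25 = 8 points per call. The objection stands, so the size is given only conditional on the phone share.

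**The direction is unknown.** The stated purpose is ketorolac against dexamethasone, and nothing in the documents shows that a caller would favour one active drug over the other. This stands too; no direction is claimed here.

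**Patients who miss visits are often the ones who feel better.** A reader might add this to the interviewer bias. It is a separate problem of selective follow-up, which posting the form to the same patients would not cure. Methods also does not confine calls to patients who miss visits.

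**Moving to mail as the default could cost data.** This is a fair warning. Missed visits are expected, the first post-operative assessment has a window ending on day 3, and the Statistical Analysis Plan closes by saying that poor follow-up prevented any analysis. Mail should therefore remain an option.

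**Conclusion.** The concern holds in limited form. As written, the plan lets someone who knows the arm take the patient-reported primary outcomes by telephone, with no safeguard on how items are read or answers recorded. This is an avoidable opening for interviewer bias.

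Its size cannot be derived from the documents. For assumed shifts of 0.1 to 0.5 SD per call in one arm, the illustrative ANOVA false-positive rate is about 5.1% to 6.9% with a quarter of forms by phone, 5.3% to 13% with half, and 6.2% to 42% with all. These ranges rest on the assumed shift and phone share, on that share being equal across arms, and on there being no true effect.

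A reader might conclude that the trial's results were biased. The documents do not support that: single blinding is openly declared, self-completion in clinic or by mail is available, and no analysis was completed. This is an inexpensive improvement to the design, relevant if the protocol or its data are reused.

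**What to change.** - **Design:** amend the blinding statement so that the assignment is known only to the operating team and the coordinator who tracks assignments.
- **Methods, who calls:** have phone questionnaires taken, where feasible, by existing personnel who have not been told the assignment and who do not carry out the chart review. That review covers medications and could reveal the arm.
- **Methods, how:** read every item and response option verbatim and record the answer as given.
- **Methods, mail:** keep mailed self-completion as an option, not the default.
- **Form and analysis plan:** add one field for mode (clinic, mail, phone) and report mode descriptively by arm. With 25 per arm over three modes, about 8 per cell if evenly spread, outcome comparisons by mode would tell little.

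**Cost:** protocol wording and one form field. The practical burden is keeping knowledge of the allocation separate from questionnaire calls within the existing team. The documents give no team size, so this may not always be possible, hence the words where feasible. The change does not remove differences between phone and paper completion, or bias from selective follow-up.
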